6.9. Concomitant Therapy

6.9.1. Permitted Medications and Non-Drug Therapies

All concomitant medications taken during the study will be recorded in the eCRF as well as the ICS usage in the past 12 months prior to Visit 1 and other additional controllers in the past 3 months prior to Visit 1. The minimum requirement is that drug name and the dates of administration are to be recorded. However, for ICS and OCS, the dose must be recorded as well as any dose changes.

All additional asthma medications such as LABA, theophyllines or anti-leukotrienes will be continually used with the same dose and regimen if they have been taken regularly in the 3 months prior to randomization (Visit 2, Week 0). Maintenance OCS will be permitted. SABAs and SAMAs are permitted as long as they are withheld for at least 6 hours prior to clinic visit.

If for any reasons (except asthma exacerbation) the participant must change their maintenance asthma treatment medications, the investigator must discuss the change with the Medical Monitor prior. Any changes of maintenance asthma treatment should be recorded in the eCRF.

Continuous Positive Airway Pressure (CPAP) for the treatment of obstructive sleep apnea is permitted, if initiated prior to the Screening Visit. This treatment must be captured in the eCRF.

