7. STUDY ASSESSMENTS AND PROCEDURES

7.1. Screening and Critical Baseline Assessments

Subjects should conduct the pre-screening visit (Visit 0) up to 28 days prior to the screening visit (Visit 1). A subject number will be assigned at this time of signing informed consent. During the pre-screening Visit, study designated personnel should provide informed consent, and pharmacokinetics (PK) informed consent to potential study participants. Site staff will review with the subject any study related procedures that must be taken prior to the next visit (i.e., withholding of short-acting beta-2-agonists (SABAs), short-acting muscarinic antagonists (SAMAs) for 6 hours and withholding of asthma medication on the morning of Visit 1, etc).

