7.2.4. Pulmonary Function Testing including Reversibility

Spirometry will be conducted, using the site's own equipment at the visits specified in the Schedule of Activities (Section 1.2). The spirometer should meet American Thoracic Society standards and produce a printout of all data generated, which should be stored in the subject's notes. The spirometer should be calibrated in accordance with the manufacturer's instructions and a calibration log maintained. Spirometry must be performed at the same time (± 2 hour) of the Visit 2 spirometry. Subjects should try to withhold SABAs or SAMAs for ≥ 6 hours and LABAs for ≥ 12 hours prior to clinic visit, if possible. Assessments to be recorded will include FEV₁, FVC. Pre-bronchodilator measurements will be taken at each clinic visit. In addition, at visit specified in the Schedule of Activities (Section 1.2) post-bronchodilator values will be recorded following standard reversibility testing. For subjects unable to achieve $\geq 12\%$ reversibility and 200 mL change at Visit 1, reversibility can be repeated at Visit 2. Further details of spirometry and reversibility testing procedures are presented in the Study Reference Manual.

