
 Least-square (LS) means and LS mean change from baseline values for each treatment group will be presented with their associated standard errors as well as 95% CIs. The estimated treatment difference along with corresponding standard error, 95% CI for each Visit will be presented.

Endpoint / Variables

 The LS mean treatment differences (and associated 95% CIs) for all visits will also be presented graphically.
Missing data imputation
The analysis using the MMRM model assumes that missing data is missing at random (MAR).
Sensitivity and Supportive Analyses

 The sensitivity analyses of the repeated measures analyses will be performed for the FEV1 key secondary endpoint using multiple imputation methods under MAR based on pattern mixture models. The method is analogous to the multiple imputation of exacerbation events. A supportive analysis of the repeated measures pre-bronchodilator FEV1 analysis will be performed, excluding all values captured within 6 hours of a SABA being administered or 12 hours of a LABA being administered to the subject. Another supportive analysis will be repeated using the “Per-protocol” analysis population
Additional estimands
A supplementary analysis will be performed using the “treatment policy” strategy for the intercurrent event of discontinuation of treatment. This analysis will include both on-treatment and off-treatment value. For missing data imputation, the missing data are assumed as MAR.

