6.1.4. Prior and Concomitant Medications

The proportion of subjects reporting each concomitant medication will be presented. Multi-ingredient medications will be presented according to their combination ATC classification rather than the classifications of the ingredients. Summaries will be split into asthma and non-asthma concomitant medications, as well as into those taken pre-treatment, during treatment and post-treatment. Asthma medications will be grouped for Respiratory Medications Classes as well, which are based on pre-defined code lists derived from ATC classifications:

- Androgens and Estrogens
- Anti-IgE, Anti-IL5
- Antiinfectives (antibiotics, antiseptics)
- Antimycotics
- Antivirals
- Beta 2 Agonist
- Corticosteroid
- Leukotriene Receptor Antagonist
- Long-acting anticholinergic

- Long-acting beta-2 agonist – Group 2 (Once per day)
- Long-acting beta-2 agonist – Group 3 (Twice per day)
- Mucolytics
- Nedocromil or Cromolyn Sodium
- Oxygen
- PDE4 Inhibitors
- Short-acting anticholinergic
- Short-acting beta-2 agonist
- Theophylline
- Xanthine

Classification of a medication as pre-, on- or post-treatment will be made with reference to the study treatment start and stop dates and the medication start date. If the medication start date is missing or partial then the medication will be considered on-treatment unless there is evidence to the contrary (e.g. the month of the start date is present and is less than the month of the first dose of study medication). Medications with a start date of up to 4 weeks after the last dose of treatment will be considered on-treatment. Medications with a start date after this period will be considered post-treatment.

Pre- and on-treatment respiratory medications will be summarised separately.

A medication will be summarised in every period (pre/on-/post) in which it was taken, so a medication that was started in the run-in and stopped during active treatment will appear in both the pre-treatment and the during treatment tables.

The listings of all asthma and non-asthma concomitant medications will be provided.

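### The supportive pre-bronchodilator FEV1 analysis excludes values taken soon after a SABA or LABA but omits SAMAs, to which the protocol applies the same 6-hour withholding as SABAs

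*SAP*

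**What the plan says.** Change from baseline in clinic pre-bronchodilator FEV1 at Week 52 is listed among the key secondary endpoints in SAP 4.3.1. SAP 4.3.2 analyses it with a repeated-measures model, then adds a supportive run "excluding all values captured within 6 hours of a SABA being administered or 12 hours of a LABA being administered to the subject".

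The protocol speaks to withholding in three places:

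- Section 7.2.4, on spirometry: "Subjects should try to withhold SABAs or SAMAs for ≥ 6 hours and LABAs for ≥ 12 hours prior to clinic visit, if possible".
- Section 6.9.1, on permitted medication: "SABAs and SAMAs are permitted as long as they are withheld for at least 6 hours prior to clinic visit".
- Section 7.1, on preparing subjects for Visit 1, which names SABAs and also "short-acting muscarinic antagonists (SAMAs) for 6 hours".

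On what is recorded about concomitant drugs, Protocol 6.9.1 states: "The minimum requirement is that drug name and the dates of administration are to be recorded". Dose is additionally required for inhaled and oral corticosteroids. Clock time is not part of that minimum.

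**The concern.** The SAP filter uses the same two windows as Protocol 7.2.4, 6 and 12 hours, so it reads as an attempt to remove values that did not respect the withholding instruction. One of the three drug classes in that instruction is missing, and no reason is given.

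Because the spirometry section asks for withholding only where possible, some visits without it are to be expected, and this run is the one planned check on whether they matter for FEV1. If it passes over one of the classes the protocol told subjects to withhold, it does not fully test what it appears designed to test.

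**Working it through.** No figure in the plan depends on this rule, so there is nothing to recalculate. The check is a comparison of text, class by class.

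| Class | Protocol 7.2.4 (spirometry) | Protocol 6.9.1 (permitted drugs) | SAP 4.3.2 exclusion |
|---|---|---|---|
| SABA | 6 hours | 6 hours | 6 hours |
| SAMA | 6 hours | 6 hours | not named |
| LABA | 12 hours | no window stated | 12 hours |

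SABA and LABA match Protocol 7.2.4. SAMA does not.

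Next, whether the gap is closed elsewhere:

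1. *Other FEV1 analyses in SAP 4.3.2.* These are multiple imputation, the Per Protocol repeat and the treatment-policy analysis. None filters on bronchodilator timing.
2. *Per Protocol exclusions, SAP 6.2.13.* The list has no withholding criterion. It does cover prohibited medication, but SAMAs are not in the prohibited list of Protocol Table 5.
3. *Is SAMA use foreseen?* It is allowed by Protocol 6.9.1, and SAP 6.1.4 includes "Short-acting anticholinergic" among the respiratory medication classes to be summarised.

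Last, which values the omission affects. A value within 6 hours of both a SABA and a SAMA is already removed by the SABA clause. A value within 12 hours of a LABA is already removed by the LABA clause. What stays in is a value taken within 6 hours of a SAMA, with no SABA in those 6 hours and no LABA in the preceding 12.

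Applying any of the three windows needs the time of the last dose relative to spirometry. The minimum record is name and dates. The eDiary (Protocol 7.2.2) counts rescue occasions over the previous 24 hours, which cannot place a dose inside or outside 6 hours. Protocol 7.2.4 refers to the Study Reference Manual for further spirometry detail, so the times may well be collected; the protocol and SAP do not show it.

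**The case against.** The strongest reply is that the omission hardly matters. The rescue inhaler supplied is salbutamol (Protocol 6.1), so rescue taken before a visit will mostly be a SABA and is already excluded. No passage gives a frequency of SAMA use, and a listing in SAP 6.1.4 proves little: that list is a general code list that also carries anti-IgE, although omalizumab is prohibited. The analysis is supportive, the endpoint is the last of five secondaries, and the success criterion concerns the primary endpoint alone. All of this stands, and it limits the importance of the point. It does not explain why a rule that otherwise follows Protocol 7.2.4 leaves out one class.

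A reader might infer three stronger things that the documents do not support.

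- *That the analysis does contain bronchodilated values.* It can; whether it does depends on SAMA-only use shortly before spirometry, which is not reported.
- *That the treatment difference is biased.* Daily salbutamol use is an endpoint and may differ by arm, but that concerns the drug already excluded. Nothing indicates that SAMA-only use differs by arm, so no amount in millilitres can be defended. The 200 mL reversibility criterion is a threshold for response to salbutamol, not an effect size for a SAMA.
- *That the filter also fails for once-daily LABAs and long-acting anticholinergics.* The 12-hour LABA window is the protocol's own, with no once-daily exception, and the protocol sets no withholding window for long-acting anticholinergics. Protocol 6.9.1 asks that regular additional asthma medication continue unchanged, so such use would generally be present at baseline and follow-up in both arms. Wider windows would be a preference, and could remove most values from a subject who takes a once-daily agent as prescribed.

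**Conclusion.** The mismatch is real and minor. As written, the supportive analysis keeps FEV1 values taken within 6 hours of a SAMA alone, which fall short of the withholding in Protocol 7.2.4 and 6.9.1. Those two sections differ in firmness: the first asks subjects to try, the second makes withholding a condition of permitted use. They agree that SAMAs and SABAs share the 6-hour window, and the point rests only on that agreement.

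Its size cannot be stated from the documents. The primary analysis has no connection to it, and the main FEV1 model applies no bronchodilator-timing exclusion, so its result is the same either way. The conclusion assumes that the SAP filter was meant to reflect the protocol's withholding instruction, which the identical windows suggest but the SAP does not say.

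**What to change.** In SAP 4.3.2, extend the first clause of the exclusion so that it removes any FEV1 value recorded within 6 hours of a SABA or a SAMA, and leave the 12-hour LABA clause as it is. If SAMAs were left out on purpose, state the reason.

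Before finalising, confirm that the time of last SABA, SAMA and LABA use before each spirometry session is in the database. If it is not, none of the three windows can be applied reliably, and the SAP should say how values with unknown timing are handled.

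The cost is a short SAP edit, a small programming change and slightly fewer values in a supportive analysis. If dose times were not collected, the SAP edit cannot recover them.

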4.4. Other Analyses

Endpoint(s)

 Mean change from baseline compared to placebo in Asthma Control Questionnaire (ACQ-5) score at Week 52 The ACQ-5 is a 5-item questionnaire developed as a measure of patient's asthma control. Response options for each question are on a 7-point scale ranging from 0 (CCI [REDACTED]) to 6 (CCI [REDACTED]). The questions are equally weighted, and the ACQ-5 score is calculated as the mean of the 5 questions, ranging between 0 (CCI [REDACTED]) to 6 (CCI [REDACTED]), where higher scores indicate worse asthma control. Mean change from baseline in clinic post-bronchodilator FEV1 at week 52
Model Specification, Checking & Diagnostics, Results, Presentation

 MMRM These endpoints will be analyzed using a mixed models repeated measures analysis (MMRM) adjusting covariates: baseline, baseline maintenance OCS therapy (OCS vs. no OCS), exacerbations in the year prior to the study (as an ordinal variable), baseline % predicted FEV1, treatment and visit, plus interaction terms for visit by baseline and visit by treatment group. A dataset om_dataset will be constructed to reflect the data structure of no missing observations

Missing data imputation

For a given visit, if the response to one of the 5 questions is missing then the ACQ-5 score will be calculated as the mean of the available responses. If the response to more than one question is missing, then the ACQ-5 score will be set to missing.
 
The analysis using the MMRM model assumes that missing data is missing at random (MAR).

Endpoint(s)

 Percent of subjects evaluated as responders as measured by ACQ-5 score at Week 52 ACQ-5 score responder is defined as the participant achieving a ≥ 0.5-point improvement (decrease) from baseline in ACQ-5 score. Percent of subjects evaluated as responders as measured by SGRQ score at Week 52 SGRQ responder is defined as ≥ 4 points improvement (decrease) from baseline in total score.
Missing data imputation
Subjects with missing values at Baseline will be excluded from analyses. Any missing values at post-baseline visit will be included as non-responders.
Model Specification, Checking & Diagnostics, Results, Presentation

 Analysis will be performed using a logistic regression model adjusting for baseline, treatment group, baseline maintenance OCS therapy (OCS vs. no OCS), number of exacerbations in previous year (as an ordinal variable), baseline disease severity (as % predicted FEV1) and baseline score. For the baseline covariate, if the factor of baseline covariate fails to converge, it will be removed from the logistic model. If the model fails to converge, e.g. due to the limited event number, then the endpoints will be analysed by Fisher exact test only. The number and percentage of patients identified as responders, non-responders or with missing data at Week 52 will be displayed for each treatment group. The model estimated ratio of the odds of being a responder in the mepolizumab treatment group compared to placebo will be presented with 95% confidence intervals and the associated p-value.

Endpoint(s)

 Percent of subjects recording a favorable treatment response as measured by the Subject Rated Response to Therapy at Week 52. Percent of subjects evaluated as having a favorable treatment response as measured by the Clinician Rated Response to Therapy at Week 52
Missing data imputation

 Subjects with missing values at Week 52 will not be imputed and will be included in the analysis as category of significantly worse.

Endpoint(s)
Model Specification, Checking & Diagnostics, Results, Presentation

 These endpoints will be analyzed using a proportional odds model (multinomial (ordered) logistic generalized linear model), with terms for treatment group, baseline maintenance OCS therapy (OCS vs. no OCS), number of exacerbations in previous year (as an ordinal variable), baseline disease severity (as % predicted FEV1). The number and percentage of patients identified as each category (including missing data) at Week 52 will be displayed for each treatment group. The model estimated ratio of the odds of being a responder in the mepolizumab treatment group compared to placebo will be presented with 95% confidence intervals and the associated p-value.

Endpoint(s)

 Mean change from baseline in daily salbutamol/albuterol use Mean change from baseline in daily asthma symptom scores Mean change from baseline in awakening at night due to asthma symptoms requiring rescue medication use Mean change from baseline in morning PEF
Missing data imputation
No imputation will be done for missing data.
Model Specification, Checking & Diagnostics, Results, Presentation

 These endpoints will be summarized by descriptive statistics: mean, SD, median, min and max. The daily data (excluding days with missing data) will be aggregated over 4-week periods (weeks 1-4, 5-8, ..., 48-52). Data for each 4-week period, and change from baseline for each 4-week periods will be summarized by treatment group.

Endpoint(s)

 Mean number of days with oral corticosteroids taken for clinically significant exacerbations Total prednisone (or equivalent) exposure for clinically significant exacerbations over the 52-week treatment period
Missing data imputation
Only the observed data before discontinuation of study treatment will be used and no imputation will be done for missing data.
Model Specification, Checking & Diagnostics, Results, Presentation

 Total number of days of oral corticosteroids use for clinically significant exacerbations per subject will be summarised by treatment arm

Endpoint(s)

 Total prednisone equivalent dose per clinically significant exacerbation per subject will be summarised by treatment arm. A summary table for OCS only and OCS plus other systemic routes of administration (oral, IV and IM) corticosteroids will be produced

Endpoint(s)

 Frequency of all exacerbations
Missing data imputation
The method for missing data imputation will be the same as the primary efficacy analysis (see Section 4.2.1 for details).
Model Specification, Checking & Diagnostics, Results, Presentation

 These endpoints will be analyzed using the same methodology as the primary analysis in Section 4.2.1

Endpoint(s)

 Time to first exacerbation Time to withdrawal from study treatment due to asthma exacerbations Time to first exacerbation requiring hospitalization or ED visit
Model Specification, Checking & Diagnostics, Results, Presentation

 These endpoints will be analyzed using the same methodology as the analysis of time to first clinically significant exacerbation in Section 4.3.2.

Endpoint(s)

 Unscheduled healthcare resource utilization (for clinically significant exacerbations and other asthma related health care) over the 52-week treatment period
Missing data imputation
No imputation will be done for missing data.
Model Specification, Checking & Diagnostics, Results, Presentation

 Healthcare resource use due to a clinically significant exacerbation and other asthma related health care will be summarized by treatment group

Endpoint(s)

 Days of school/work missed
Missing data imputation
No imputation will be done for missing data.

Model Specification, Checking & Diagnostics, Results, Presentation

- Number of days off school/work due to asthma symptoms for different groups will be summarized by mean, SD, median, minimum and maximum.

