
 • To evaluate the effects of mepolizumab compared with placebo on asthma control 	
 • Mean change from baseline compared to placebo in Asthma Control Questionnaire (ACQ-5) score at Week 52 • Percent of subjects evaluated as responders as measured by ACQ-5 score at Week 52 • Percent of subjects evaluated as responders as measured by SGRQ score at Week 52 • Percent of subjects recording a favourable treatment response as measured by the Subject Rated Response to Therapy at Week 52 • Percent of subjects evaluated as having a favourable treatment response as measured by the Clinician Rated Response to Therapy at Week 52 • Mean change from baseline in daily salbutamol/albuterol use • Mean change from baseline in daily asthma symptom scores • Mean change from baseline in awakening at night due to asthma symptoms requiring rescue medication use • Mean change from baseline in morning PEF • Mean change from baseline in clinic post-bronchodilator FEV1 at Week 52 • Mean number of days with oral corticosteroids taken for clinically significant exacerbations • Total prednisone (or equivalent) exposure for clinically significant exacerbation over the 52-week treatment period • Frequency of all exacerbations • Time to first exacerbation • Time to withdrawal from study treatment due to asthma exacerbations • Time to first exacerbation requiring hospitalization or ED visit

Objectives	Endpoints
	
 Unscheduled healthcare resource utilization (for clinically significant exacerbations and other asthma related health care) over the 52-week treatment period Mean days of School/Work missed over the 52-treatment period
Pharmacodynamics	

 To evaluate the PD of SC mepolizumab in Chinese subjects with severe asthma with eosinophilic airway inflammation 	
 Blood eosinophil ratio to baseline
PK Sub-Study	

 To evaluate the PK of SC mepolizumab in Chinese subjects with severe asthma with eosinophilic airway inflammation 	
 PK parameter estimates of mepolizumab

Primary estimand

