4.2. Primary Endpoint(s) Analyses

4.2.1. Main analytical approach

The primary efficacy analysis will evaluate the primary estimand in the Modified Intent-to-Treat population, by first using a generalized linear model with a log-link function to get an estimate of the logarithm of the rate ratio for mepolizumab vs. placebo and associated standard error. These estimates will then be combined with the global MEA115588 study using the pre-specified robust mixture prior to obtain the posterior distribution for the China rate ratio (on the log scale). A 95% posterior probability that the true rate ratio < 1 represents a high level of confidence for declaring a positive treatment benefit in Chinese patients in the context of a bridging study where substantial evidence of treatment benefit in global (non-Chinese) patients already exists.

Model Specification

- Generalized linear model assuming a negative binomial distribution
- Terms in the model:
 - Response:** number of recorded, on-treatment, clinically significant exacerbations experienced per subject.
 - Categorical:** treatment group, baseline maintenance OCS therapy (OCS vs. no OCS),
 - Continuous:** baseline disease severity (as % predicted FEV₁), number of exacerbations in previous year (as an ordinal variable)
 - Offset:** logarithm of time on treatment

Since this is a bridging study, to ensure comparability between results in MEA115588 and this study, the analysis model including the covariates are the same with MEA115588.

Model Results Presentation

- Treatment group model estimated exacerbation rates, the treatment rate ratio and associated SE and 95% CI will be presented.
- The pairwise treatment rate ratios and associated 95% CIs will also be presented graphically

Bayesian Dynamic Borrowing

A Bayesian dynamic borrowing model ([Schmidli](#), 2014) will be used to make inference about the logarithmic rate ratio of exacerbations in mepolizumab 100mg SC to Placebo in Chinese participants. The prior distribution will be a mixture with two components: the first component is based on the results from the MEA115588 study; the second component is a vague distribution centred on 0 representing 'no-effect'.

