6.2.3. Study Period

Assessments and events will be classified according to the time of occurrence relative to the study treatment period.

Study treatment period for Exacerbation

Treatment period	Definition
Pre-Treatment	Event start date < IP start date
On-Treatment	Subjects who did not withdraw early from IP: Event onset date is on/after IP start date & on/before the end of analysis period. (IP Start Date \leq Event Start Date \leq end of analysis period) Subjects who withdrew early from IP: Event onset date is on/after IP start date & on/before the earlier of the IP stop date+28 days/end of analysis period. (IP Start Date \leq Event Start Date \leq IP Stop Date + 28 days/end of analysis period)
Off-Treatment	Event onset date is after IP stop date +28 days and on/before the end of analysis period. (IP Stop Date + 28 days < Event Start Date \leq end of analysis period)
Post-Treatment	Event onset date is after the end of analysis period. (Event Start Date > end of analysis period)

Note: the IP stop date is missing or the event start date is missing then the event considered on-treatment

Study Treatment Period for Visit Based Efficacy Assessments

Applicable to all visit-based efficacy assessment such as FEV1, SGRQ, ACQ, Subject Rated Response to Therapy, Clinician Rated Response to Therapy.

Treatment period	Definition
Pre-Treatment	Visit date < IP start date
On-Treatment	Subjects who did not withdraw early from IP: Visit date is after IP start date & on/before the end of analysis period. (IP Start Date < Visit Date \leq end of analysis period) Subjects who withdrew early from IP: Visit date is after IP start date & on/before earlier of the IP stop date +28 days/end of analysis period. (IP Start Date < Visit Date \leq earlier of IP Stop Date + 28 days/end of analysis period)
Off-Treatment	(IP Stop Date + 28 days < Visit Date \leq end of analysis period)
Post-Treatment	Visit Date > end of analysis period

Study treatment Period for Adverse Events

Treatment period	Definition
Pre-Treatment	Event start date < IP start date
On-Treatment	IP start date \leq Event start date \leq IP stop date +28 days
Post-Treatment	Event start date > IP stop date +28 days

Note: the IP stop date is missing or the event start date is missing then the event considered on-treatment

Study Treatment Period for Visit Based Safety Assessments

Applicable to all safety assessment such as vital signs, ECG, laboratory assessments:

Treatment period	Definition

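### SAP 4.4 summarises prednisone dose per exacerbation, although the endpoint is the total dose over 52 weeks

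*SAP*

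**What the plan says.** SAP 1.1 lists among the other endpoints "Total prednisone (or equivalent) exposure for clinically significant exacerbation over the 52-week treatment period". SAP 4.4 repeats it above the analysis text and then plans three descriptive lines for the two steroid endpoints.

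- Dose: "Total prednisone equivalent dose per clinically significant exacerbation per subject will be summarised by treatment arm".
- Days: "Total number of days of oral corticosteroids use for clinically significant exacerbations per subject will be summarised by treatment arm".
- Route: a table for oral steroids alone and for all systemic routes together. This splits the data by route and defines no total.

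The missing-data rule for both endpoints is "Only the observed data before discontinuation of study treatment will be used and no imputation will be done for missing data". SAP 4.4 gives no offset, no annualisation and no rule for subjects without an exacerbation.

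The 52-week total is not defined elsewhere. SAP 6.2.14 converts steroids to prednisone equivalents and adds overlapping courses on the same day, which yields a daily dose. It does not sum over a subject's exacerbations or over the year. Protocol 9.4.1.3 leaves the other efficacy endpoints to the analysis plan, and SAP 4.9 declares no change from the protocol.

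The primary analysis treats time differently. SAP 4.2.1 uses as offset the "logarithm of time on treatment". For subjects who stop study drug early, SAP 6.2.3 counts exacerbations that start "on/before the earlier of the IP stop date+28 days/end of analysis period".

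**The concern.** Steroid exposure can fall because there are fewer exacerbations or because each one needs less steroid. A 52-week total captures both. A dose per exacerbation captures only the second, and mepolizumab is expected to act mainly on the first. The per-event figure also exists only for subjects who had an event, so it compares subsets selected by a post-randomisation outcome that treatment itself affects. A reader who takes the table as the result for the listed endpoint could conclude that steroid exposure was unchanged when it had fallen in step with the exacerbation rate.

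The time cut is a separate matter. A subject who stops early contributes a short period to an unadjusted total as though it were the full year. An exacerbation in the 28 days after the last dose counts in the primary endpoint, but its steroid course may not count here.

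**Working it through.** **Inputs.** SAP 5.1 and 5.2 give rates of 0.975 (placebo) and 0.585 (mepolizumab) per year, dispersion k = 1.6, 128 evaluable subjects per arm, and 44 of 300 subjects (14.7%) allowed for drop-out. The documents give no figure for steroid dose per exacerbation and no discontinuation by arm, so both are assumed below.

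**The plan's own figure.** The SAP states 66% power at these rates.
- V = 1/0.975 + 1/0.585 + 2 × 1.6 = 1.026 + 1.709 + 3.2 = 5.935, with square root 2.436.
- z = √128 × |ln 0.60| / 2.436 − 1.96 = 11.314 × 0.5108 / 2.436 − 1.96 = 0.41, which gives 66.0%.

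The figure is reproduced, so the rates and dispersion are read as the SAP uses them.

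**Subjects with no exacerbation in a full year.** P(0) = (1 + kμ)^(−1/k).
- Placebo: (1 + 1.6 × 0.975)^(−0.625) = 2.56^(−0.625) = 0.556, so 44.4% have an event.
- Mepolizumab: (1 + 1.6 × 0.585)^(−0.625) = 1.936^(−0.625) = 0.662, so 33.8% have an event.

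A dose per event is defined only for those 44% and 34%.

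**Mepolizumab/placebo ratio under each summary.** Let r be the ratio of mean dose per event, the same for every event within an arm.

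| Summary | Formula | r = 0.9 | r = 1.0 | r = 1.1 |
|---|---|---|---|---|
| Dose per exacerbation (SAP 4.4, literal) | r | 0.90 | 1.00 | 1.10 |
| Total dose per subject, zeros included (the endpoint) | r × 0.585/0.975 | 0.54 | 0.60 | 0.66 |

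Whatever r is, the two differ by the factor 0.60, which is the assumed effect on exacerbations.

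**Oral corticosteroid days.** This line is a per-subject total. With equal days per event and zeros for event-free subjects, the ratio is 0.585/0.975 = 0.60. If event-free subjects were left out, it would be (0.585/0.338) / (0.975/0.444) = 1.731/2.196 = 0.79. The zero rule therefore matters here too, and the SAP does not state it.

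**Cut at discontinuation with no time adjustment.** Suppose a fraction d of an arm stops, uniformly over the year. Mean time is then 1 − d/2, and the ratio of unadjusted totals is 0.60 × (mepolizumab time / placebo time).
- 14.7% in both arms: 0.60 × 0.927/0.927 = 0.60.
- 20% placebo, 10% mepolizumab: 0.60 × 0.95/0.90 = 0.63.
- 10% placebo, 20% mepolizumab: 0.60 × 0.90/0.95 = 0.57.
- 30% placebo, 5% mepolizumab: 0.60 × 0.975/0.85 = 0.69.

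A gamma-Poisson simulation with 1,000,000 subjects per arm agrees with these to within about 0.003, and dividing by person-time returns about 0.60 in each case. For one subject with a last dose at Week 12, the on-treatment time under SAP 6.2.4 is (84 + 28 + 1)/365.25 = 0.31 year.

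**The case against.** The strongest reply is that the dose line is a slip. It begins with a total and ends per subject, it sits under an endpoint that is a 52-week total, and SAP 4.9 says nothing has changed. Replacing one preposition would give a per-subject sum. That is plausible. But the neighbouring days line speaks of use for exacerbations per subject, and the dose line does not follow it, so the literal reading is per event. Two programmers could produce different tables, and the text needs correcting on either reading.

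A reader might infer that the trial would show no steroid saving at all. The documents do not support that, because the days summary in the same block is a per-subject total and would show the saving if zeros are counted. A reader might also infer that the cut at discontinuation hides the saving or biases the comparison. It does neither by itself. With equal discontinuation the ratio stays at 0.60, and under the assumed unequal splits it moves to between 0.57 and 0.69.

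Three further replies stand. The SAP nowhere says that event-free subjects are excluded; this follows only from the per-event reading, and SAP 3 names MITT as the primary population for all efficacy analyses. The days endpoint is not defined as a rate, so annualising it is a refinement. Restricting the data to time on treatment is also broadly in line with the on-treatment approach of the primary analysis.

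**Conclusion.** The point holds for the prednisone dose summary. Read literally, it does not estimate the listed 52-week total, and nothing else in the SAP supplies that total. At the SAP's rates, with equal dose per event in both arms, it would show a ratio of 1.00 where the total-dose ratio is 0.60, and it would cover about 44% of placebo and 34% of mepolizumab subjects over a full year. The 1.00 rests on the equal-dose assumption; the factor of 0.60 between the two summaries rests only on the assumed rate ratio and does not depend on the dose ratio r.

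The missing time adjustment is a lesser point. It distorts the comparison only if discontinuation differs between arms, and the splits used to size it are assumptions.

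Severity is low. Both are descriptive other endpoints outside the success criterion, and the primary analysis estimates the reduction in exacerbations directly.

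**What to change.** In SAP 4.4:

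1. Summarise, for every MITT subject, the total prednisone-equivalent dose and the total oral corticosteroid days for clinically significant exacerbations, with zero for subjects who had none.
2. Take both over the on-treatment window for exacerbations in SAP 6.2.3, in place of the less exact cut "Only the observed data before discontinuation of study treatment will be used", and say how a steroid course that runs past the end of the window is counted.
3. Report also, by arm, the sum of dose (or days) divided by the sum of on-treatment years from SAP 6.2.4. Pooling within arm avoids unstable individual rates from short follow-up.
4. Keep dose per exacerbation as a supplementary descriptive line, labelled as covering only subjects with an event.

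The cost is SAP wording and one derived variable from data already collected. The change should be made before unblinding.
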